Study Protocol

Protocol ID: 2025ZSLYEC-728

Title: Efficacy and Safety of the RDI Mode in Endoscopic Submucosal Dissection: a Multicenter, Randomized Controlled Study

Document date: 12,1, 2025

Background and aim

Conventional white-light endoscopy (WLE) is hampered by insufficient contrast when attempting to identify deep vessels and active bleeding sites; visibility drops further when blood pools or spurts obscure the field, resulting in significantly lower hemostatic efficiency. Red dichromatic imaging (RDI), a novel image-enhanced endoscopic modality, has recently been shown to improve the visualization of deep-lying vessels and bleeding points, shorten hemostasis time and potentially increase overall procedural efficiency.

Although retrospective series have suggested that RDI may facilitate intra-operative bleeding control and better delineation of the submucosal plane during endoscopic submucosal dissection (ESD), high-level evidence from multicenter, randomized, controlled trials (RCTs) is lacking. No study has yet demonstrated superiority over WLE with respect to critical endpoints such as en-bloc resection rate, procedure time, complication rate and operator mental workload.

We therefore designed a multicenter RCT to systematically compare the efficacy and safety of full-procedural RDI with conventional WLE during ESD.

Methods

Study design: a multicenter, randomized controlled clinical trial.

Location: The Sixth Affiliated Hospital, Sun Yat-sen University, Guangdong Provincial Hospital of Chinese Medicine, Guangdong Second Provincial General Hospital

The inclusion criteria:

- ① Age \geq 18 years.
- ② Early gastric cancer or precancerous lesions, early esophageal cancer or precancerous lesions, or early colorectal cancer/polyps that meet ESD indications.
- ③ ESD procedure to be performed at a participating center.
- ④ Lesion diameter 20–60 mm.
- ⑤ Written informed consent provided voluntarily.

The exclusion criteria:

- ① Foreigners.
- ② Severe coagulopathy (platelet count $<50 \times 10^9/L$ or INR >1.5), significant cardiopulmonary disease, or any other contraindication to endoscopic therapy.

③ Imaging evidence of distant metastasis or lymph-node metastasis.

Intervention

Patients who met the inclusion and exclusion criteria were randomly assigned to either the RDI group or the conventional white-light endoscopy (WLE) group. In the RDI group, the submucosal dissection was performed entirely under RDI mode (white-light mode was allowed only for observation and marking). In the WLE group, the entire ESD procedure was completed with white-light mode without switching to RDI. All ESD procedures were performed by experienced endoscopists (≥ 300 previous ESD cases and formal RDI training, with ≥ 20 ESD cases performed under RDI mode).

Outcome parameters

The primary outcome parameter is the mean resection speed (mm^2/min) achieved with RDI versus conventional WLE during ESD.

The secondary outcome parameters are: complete resection (R0) rate, en-bloc resection rate, resection margin, number of intra-procedural bleeding episodes, intra-procedural blood loss, intra-procedural hemostasis time, other intra-procedural adverse events, and post-procedural adverse events.

The results will be analyzed in full analysis set, per-protocol set and safety set.

After the overall analysis, all data will be stratified by lesion location and analyzed separately for esophageal, gastric, and colorectal subgroups.

Definitions

The mean resection speed is the result of resection area divided by the resection time. The resection area is defined as the area on the specimen-fixation board. The resection time is defined as the time from the first mucosal incision to complete dissection of the lesion. Adverse events included bleeding, perforation, infection, and so on, mentioned by Cotton et al. (Gastrointest Endosc. 1994;40:514-518).

Sample Size

Based on a pilot study of 20 cases at our center, the mean resection speed in the RDI group was $27.2 \pm 9.8 \text{ mm}^2/\text{min}$ versus $21.1 \pm 12.2 \text{ mm}^2/\text{min}$ in the white-light group.

Assuming H_0 : no difference in mean resection speed between the two groups, and setting $\alpha = 0.05$ and power = 0.90, the required sample size is 71 lesions per arm (142 total).

Allowing for a 10 % dropout rate, we plan to enroll 79 lesions per arm, yielding 158 lesions in total (each lesion requiring ESD is counted as one case, even if multiple lesions occur in the same patient).

Randomization

Stratified randomization by center. Random numbers generated in Excel by an independent statistician; sequentially numbered, sealed, opaque envelopes prepared and held by the third party. The envelopes constitute the allocation sequence; random numbers remain concealed from patients and endoscopists until the envelope is opened immediately before allocation.

Blinding

Patients will be blinded; operators and video reviewers cannot be blinded; pathologists will remain blinded.

Statistical analysis

All analyses were performed with SPSS version 26. Baseline characteristics were examined to assess balance across concentration groups. Normally distributed continuous variables are presented as mean \pm SD and compared between groups using independent-samples t-tests; non-normally distributed continuous variables are expressed as median (interquartile range) and compared with the Wilcoxon rank-sum test. Categorical rates were compared using the χ^2 test. A two-sided $P < 0.05$ was considered statistically significant.

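### Separate tests in esophageal, gastric and colorectal lesions do not show whether the RDI effect differs by organ; one arm-by-location model with exploratory organ estimates would be a cheap improvement (low severity)

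*Protocol*

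**What the plan says.** Under Outcome parameters, the protocol states: "After the overall analysis, all data will be stratified by lesion location and analyzed separately for esophageal, gastric, and colorectal subgroups". The plan covers all data, so it takes in the secondary outcomes as well as resection speed.

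The Statistical analysis section names three methods, each a two-group comparison. Normally distributed continuous variables are "compared between groups using independent-samples t-tests", other continuous variables are "compared with the Wilcoxon rank-sum test", and "Categorical rates were compared using the χ^2 test". A single threshold follows: a two-sided P below 0.05 "was considered statistically significant". It is not said to exclude the organ subgroups.

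Under Randomization, the protocol says "Stratified randomization by center"; lesion location is not a stratum. The Sample Size section gives 71 lesions per arm for the overall comparison and no figure by organ.

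**The concern.** A P value within the esophagus answers whether RDI and WLE differ in the esophagus. Three such P values side by side do not answer whether the RDI effect differs between organs. For that, the difference between the organ effects has to be estimated with its own standard error.

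Each organ holds only part of a sample that was sized for the whole. If RDI works equally well everywhere, some organs may pass 0.05 and others miss it because of subgroup size and chance alone. A report that lists the three verdicts invites the reading that RDI helps in one organ and not in another. That reading could steer practice by organ without evidence of any difference. The pooled primary result is not at stake.

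**Working it through.** **Inputs from the protocol (Sample Size):** pilot 27.2 ± 9.8 mm²/min with RDI and 21.1 ± 12.2 with WLE, two-sided α 0.05, power 0.90, 71 lesions per arm.

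**Assumptions, because the protocol gives no figure:** the organ mix, the SD within an organ, and independent lesions. On the last, the protocol notes that "each lesion requiring ESD is counted as one case, even if multiple lesions occur in the same patient".

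**1. The plan's own figure.** Difference = 27.2 − 21.1 = 6.1. SD = √((9.8² + 12.2²)/2) = √122.44 = 11.07. Noncentral-t power is 0.8995 at 70 per arm and 0.9035 at 71, so 71 per arm reproduces. With 10% dropout, 71/0.9 = 78.9, which rounds up to 79. The pooled sample size stands.

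**2. Power within each organ under a uniform effect.** For n lesions per arm in an organ, the noncentrality is 6.1/(11.07·√(2/n)) with 2n − 2 degrees of freedom. With p the power in each organ, the chance of a mixed pattern (at least one organ significant and at least one not) is 1 − Πp − Π(1 − p).

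| Assumed mix (lesions per arm) | Power by organ | Mixed pattern |
|---|---|---|
| Equal thirds (23.67 each) | 0.459 each | 0.745 |
| 50/30/20% (35.5, 21.3, 14.2) | 0.629, 0.419, 0.293 | 0.771 |
| 50, 14 and 7 | 0.779, 0.290, 0.158 | 0.832 |

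For equal thirds: 1 − 0.459³ − 0.541³ = 1 − 0.097 − 0.159 = 0.745 with unrounded powers.

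**3. Sensitivity with equal thirds.**
- Uniform effect of 2, 4, 8 or 10 mm²/min at SD 11.07: 25%, 53%, 65%, 36%.
- Location explains a share f of the variance, so the within-organ SD is 11.07·√(1 − f), effect 6.1: 73% at f = 0.25, 57% at f = 0.5, 21% at f = 0.7.
- Both changed together: 2% (effect 8, f = 0.7) and 3% (effect 10, f = 0.5).

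The 21% is therefore not a lower limit. The chance of a mixed pattern can be very small when the effect is large and the organs account for much of the spread.

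**4. What one model would deliver.** With three centers, residual df = 142 − 6 − 2 = 134 and t = 1.978. The approximate 95% CI half-width for an organ is 1.978 × 11.07 × √(2/n):
- equal thirds: 6.4 mm²/min in each organ;
- 50/30/20%: 5.2, 6.7 and 8.2;
- 50, 14 and 7 per arm: 4.4, 8.3 and 11.7.

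Most of these exceed the planned effect of 6.1.

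**5. Power of the interaction test (2 and 134 df).** Suppose true effects of 6.1, 6.1 and 0. The noncentrality is λ = Σ wⱼ(δⱼ − δ̄)², where wⱼ = nⱼ/(2·SD²) and δ̄ is the weighted mean effect. For equal thirds, w = 23.67/244.88 = 0.0967, δ̄ = 4.07, the sum of squares is 2 × 2.03² + 4.07² = 24.8, and λ = 2.40. Power is 0.259. Depending on which organ has no effect, power is 0.196–0.287 at 50/30/20% and 0.127–0.244 at 50, 14 and 7 per arm. If location explains half the variance, the range over the three mixes is 0.214–0.527.

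**The case against.** The strongest objection is that this is silence rather than error. Interaction tests and the labelling of subgroups are commonly left to the SAP, which is not at hand. Analysing organs separately is a normal way to report them, and each within-organ test is valid for its own organ. It would be wrong only if used to compare organs, which the protocol does not say it will do.

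Much of this stands. Three stronger readings are tempting, and the protocol supports none of them:

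- **That two-group tests are fixed as the sole method for every analysis, subgroups included.** The sentence "All analyses were performed with SPSS version 26" governs the software. The tests follow in separate sentences by type of variable and are not called exhaustive, so an interaction test is not excluded.
- **That the trial intends to claim benefit in some organs and not in others.** No such claim is announced, and the organ analyses come after the overall one.
- **That the sample size or primary conclusion is flawed.** Both concern the pooled comparison, and the sample size reproduces.

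It is also fair that the 75% depends on an organ mix and SD that the protocol does not give, and that the interaction test is weak.

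The objection does not remove the point. The protocol states a method for location, namely separate analysis of all data, beside a significance rule with no subgroup exemption. A better method is available at almost no cost.

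**Conclusion.** The point holds as a low-severity suggestion. Separate within-organ tests, as written, cannot show whether the RDI effect differs by organ, and the trial is sized for the pooled comparison alone.

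At the protocol's planning values and an assumed equal-thirds mix, each organ has about 46% power. A uniform effect would then give a mixed set of verdicts about 75% of the time, or 77–83% with the uneven mixes tried. These figures illustrate the risk and do not predict the result. They rest on the assumed mix, on an SD of 11.07 within each organ and on independent lesions, and other plausible inputs bring the figure down to a few percent. Harm arises only if a reader takes a mixed pattern as a difference between organs.

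**What to change.** For resection speed, replace the separate organ tests with one linear model containing arm, location, arm-by-location and center, the last because it is the randomization stratifier. Report the interaction test. Give the RDI-minus-WLE difference in each organ with its 95% CI, labelled exploratory and without a significance verdict per organ. Report secondary outcomes by organ descriptively.

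Add one sentence saying that a non-significant interaction does not show a uniform effect. At about 13–29% power when one organ has no effect and the SD is 11.07, the test will miss many real differences. The gain is mainly protection against reading chance patterns as organ differences.

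The cost is one added model and the loss of any standalone significance claim for a single organ. No extra patients or data are needed, and the pooled analysis and sample size stay as they are.

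### Does the resection-speed definition need a rule for an ESD that is abandoned before dissection is complete?

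*Protocol*

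**What the plan says.** Under Outcome parameters: "The primary outcome parameter is the mean resection speed (mm^2/min) achieved with RDI versus conventional WLE during ESD". Under Definitions, "The mean resection speed is the result of resection area divided by the resection time". The two terms are fixed there as well: "The resection area is defined as the area on the specimen-fixation board", and "The resection time is defined as the time from the first mucosal incision to complete dissection of the lesion".

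The protocol does not mention an abandoned or converted ESD. On analysis populations it says only that "The results will be analyzed in full analysis set, per-protocol set and safety set", without defining the sets. Speed is compared by t-test, except that under Statistical analysis "non-normally distributed continuous variables are expressed as median (interquartile range) and compared with the Wilcoxon rank-sum test". The secondary outcomes include "complete resection (R0) rate, en-bloc resection rate, resection margin". Sample Size allows 10% for dropout, which takes 71 lesions per arm to 79.

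**The concern.** Read literally, the clock stops at one event only, complete dissection, and the area exists only once a specimen is mounted. A lesion whose dissection is abandoned has no end time and no complete specimen. It was randomised, yet it has no value to enter in either test, even in the full analysis set.

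The comparison would then be of speed among completed dissections. There is some reason to ask whether the losses could differ by arm. The Background expects RDI to help with bleeding control and with seeing the submucosal plane, bleeding and perforation are among the listed adverse events, and the operators are not blinded. If abandoned cases tend to be the slow ones, the arm with more of them would look faster than it was. Losses in the white-light arm would hide part of an RDI benefit, and losses in the RDI arm would create an apparent one. The 10% allowance replaces lost numbers but does not restore comparability.

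**Working it through.** **Planned size.** Inputs from Sample Size: means 27.2 and 21.1, SDs 9.8 and 12.2 mm²/min, α = 0.05 (two-sided, from Statistical analysis), power 0.90.

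- Difference = 27.2 − 21.1 = 6.1. Pooled SD = √((9.8² + 12.2²)/2) = √122.44 = 11.07.
- Normal formula: n = 2 × 122.44 × (1.960 + 1.282)² / 6.1² = 69.1, so 70 per arm. With the noncentral t, power is 0.8995 at 70 and 0.9035 at 71, so 71 per arm.
- 71 / 0.9 = 78.9, so 79 per arm. Both stated figures are reproduced and do not bear on the point.

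**Shift in a mean if its slowest lesions are lost.** The abandonment rate is not in the protocol; 2%, 5% and 10% are assumptions. Speeds are assumed to be gamma with the pilot mean m and SD s: shape k = (m/s)², scale s²/m. After the slowest fraction f is removed, the mean is m × (1 − F₍k+1₎(q_f)) / (1 − f), where q_f is the f-quantile and F₍k+1₎ is the gamma distribution function with shape k + 1 and the same scale.

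For white light, k = (21.1/12.2)² = 2.99 and the scale is 12.2²/21.1 = 7.05. At f = 5% the cut-off is 5.74 and the mean rises by 0.89, which is 0.89/6.1 = 15% of the planned difference.

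| Slowest fraction lost | White-light mean rises by | RDI mean rises by | Difference if both arms lose it |
|---|---|---|---|
| 2% | 0.37 | 0.37 | 6.09 |
| 5% | 0.89 | 0.85 | 6.05 |
| 10% | 1.74 | 1.60 | 5.96 |

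The shift matters when one arm alone loses lesions. It nearly cancels when both do.

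**Power with a true difference of 6.1** (20,000 simulated trials, gamma speeds, 79 per arm; 4 of 79 is 5.1%):

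| Lesions without a value | t-test | Wilcoxon |
|---|---|---|
| None | 0.92 | 0.98 |
| Slowest 4, white light only | 0.82 | 0.94 |
| Random 4, white light only | 0.91 | 0.98 |
| Slowest 4 in each arm | 0.91 | 0.98 |

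The only material fall needs losses confined to one arm and falling exactly on its slowest lesions. Even then the Wilcoxon test, which the protocol assigns to skewed data such as these, stays above the planned 0.90.

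**No true difference** (both arms 21.1, SD 12.2), slowest RDI lesions lost, none in white light. Chance of a significant t-test favouring RDI:

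| Lost of 79 | 0 | 1 | 2 | 4 | 8 |
|---|---|---|---|---|---|
| Favouring RDI | 2.5% | 3.4% | about 4.5% | about 7.2% | about 15% |

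The Wilcoxon test does not remove this; with 4 lost it gives about 8%.

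**Scoring abandoned lesions as zero.** With 5% zeros at random in each arm the means become 0.95 × 27.2 = 25.84 and 0.95 × 21.1 = 20.05, and the SDs 11.24 and 12.75. Noncentral-t power at 79 per arm falls from 0.93 to 0.85. In simulation, with the slowest 4 in each arm set to zero, it is 0.87; leaving the same lesions out gives 0.91. With equal true speeds and 4 random white-light lesions set to zero, about 7% of trials favour RDI on speed, although only completion differs.

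**The case for a change.** The strongest case for a change is that the endpoint definition itself, not a missing imputation rule, leaves the lesion without a value, and that an analysis plan cannot recover a stop time that sites were never asked to record. Loss could also depend on arm, because the visibility that RDI is meant to improve may decide which dissections are completed.

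The first part stands as a description: an abandoned ESD has no primary value under the wording. The point about the stop time does not carry. A score of zero or a worst rank needs only the fact that the lesion was not completed, and no clock reading enters it. The choice therefore stays open to the analysts.

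Arm-dependent loss is possible and the documents do not rule it out. Nor do they support any size for it. Eligible lesions are 20–60 mm and meet ESD indications, severe coagulopathy is excluded, and operators have at least 300 ESDs and at least 20 under RDI. That makes frequent abandonment less likely, without proving that it is rare.

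Piecemeal removal is not part of the problem. Once complete, it has an end time and a specimen area, and the en-bloc rate records it.

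**Conclusion.** No change to the plan is called for. The definition is right for the lesions it describes and conflicts with nothing in the protocol. What is unstated is how a lesion without a measurable speed is treated in the full analysis set, a detail that an analysis plan commonly supplies and that analysts can fill sensibly, with completion reported by arm and a worst-rank comparison as a sensitivity check.

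The size depends on assumptions that the protocol neither gives nor supports. Balanced loss of 4 in each arm costs about 0.01 of t-test power. One or two lost RDI lesions, all among the slowest and with none lost in white light, raise the chance of a false result favouring RDI from 2.5% to about 3.4% or 4.5%. It takes about four or more one-sided losses, all among the slowest, to reach 7% or beyond.

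The one remedy that would alter the primary result, zero or worst-rank scoring, is a trade-off. It changes what is being estimated and, on the t-test, takes power below the planned 0.90 even when the arms lose lesions equally. If abandonment proved both frequent and lopsided, the primary comparison should be read as one among completed dissections.

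### Patients are randomised but lesions are counted and tested as independent cases; with same-arm, positively correlated lesions, type I error exceeds 5% and 71 lesions per arm give less than 90% power

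*Protocol*

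**What the plan says.** Under Intervention, the unit assigned is the patient: "Patients who met the inclusion and exclusion criteria were randomly assigned to either the RDI group" or to WLE. Under Sample Size, the unit is the lesion: 71 per arm for 90% power, raised to 79 per arm for 10% dropout, with the explicit rule that "each lesion requiring ESD is counted as one case, even if multiple lesions occur in the same patient".

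Under Randomization, allocation is stratified by center and concealed "until the envelope is opened immediately before allocation". Nothing says whether an envelope belongs to a patient or to a lesion, or what happens with a patient's second lesion.

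Under Statistical analysis, normally distributed continuous variables are "compared between groups using independent-samples t-tests". Other continuous variables get the Wilcoxon rank-sum test and rates get the chi-square test. All three assume independent observations. The protocol has no limit of one lesion per patient, no within-patient correlation and no clustered method.

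**The concern.** The protocol foresees patients with several lesions and decides to count each lesion as a full case. If such a patient is allocated once, all of that patient's lesions fall in one arm. Resection speeds in the same patient may be alike, since they share patient and setting factors. Two positively correlated lesions in one arm then tell less about the arm mean than two lesions from different patients.

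Two things follow. The independent-samples test understates the standard error, so the primary comparison can reject a true null hypothesis more often than the stated 5%. And the 90% power claimed for 71 lesions per arm holds for a valid test only if there is one lesion per patient or no within-patient correlation.

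This cannot be left to a later analysis plan. The counting rule and the tests are stated in the protocol, and sites act on the unit of allocation each time they open an envelope.

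**Working it through.** **Inputs from the protocol (Sample Size; Statistical analysis).** RDI 27.2, SD 9.8; WLE 21.1, SD 12.2 mm²/min; two-sided alpha 0.05; power 0.90; 10% dropout.

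**Reproducing the stated figure.**
- Difference = 27.2 − 21.1 = 6.1.
- SD = √((9.8² + 12.2²)/2) = 11.065.
- Standardised difference = 6.1/11.065 = 0.551.
- The two-sample t solution is 70.1, rounded up to 71 per arm. Power at 71 is 90.4%.
- 71/0.9 = 78.9, so 79 per arm.

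The stated 71 and 79 are therefore the calculation for independent observations. The only inflation is for dropout.

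**Assumptions not in the protocol.** A share p of patients has two lesions, both in the same arm, and the rest have one. The within-patient correlation is ρ. Low shares are included because each extra lesion must itself qualify ("Lesion diameter 20–60 mm", and an ESD indication).

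**Formulas.**
- Design effect: DE = 1 + [(1 + 3p)/(1 + p) − 1] × ρ. The ratio is the sum of squared cluster sizes over the sum of cluster sizes.
- Type I error of the planned test: 2 × [1 − Φ(1.96/√DE)].
- Power of a valid 5% test: t-test power at 71/DE lesions per arm.

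Example, p = 0.20 and ρ = 0.5: (1 + 0.6)/(1.2) = 1.333; DE = 1 + 0.333 × 0.5 = 1.167; type I error = 2 × [1 − Φ(1.96/1.080)] = 7.0%; 71/1.167 = 60.9 per arm, power 85.5%.

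| p / ρ | DE | Type I error, planned t-test | 71/DE | Valid-test power at 71 per arm | Valid-test power if all 79 are evaluable |
|---|---|---|---|---|---|
| 0 or ρ = 0 | 1.00 | 5.0% | 71 | 90.4% | 93.1% |
| 5% / 0.3 | 1.03 | 5.3% | 69.0 | 89.5% | 92.4% |
| 10% / 0.5 | 1.09 | 6.1% | 65.1 | 87.7% | 90.9% |
| 20% / 0.5 | 1.17 | 7.0% | 60.9 | 85.5% | 89.0% |
| 40% / 0.7 | 1.40 | 9.8% | 50.7 | 78.5% | 82.7% |

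**Simulation check** (142 lesions, 20,000 runs per cell; the four clustered rows in order).

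| Allocation and analysis | Type I error | Power |
|---|---|---|
| By patient, planned t-test | 5.4, 5.9, 7.2, 10.0% | 90.0, 89.5, 88.6, 86.3% |
| By patient, patient-clustered standard errors | 5.1, 4.9, 5.3, 5.2% | 89.5, 87.9, 85.7, 78.7% |
| By patient, one index lesion per patient | not run | 88.8, 87.8, 84.7, 78.0% |
| By lesion, planned t-test | 4.9, 5.2, 5.1, 5.0% | 90.4, 90.2, 90.2, 90.4% |

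The formulas and the simulation agree. The planned test fails only when a patient's lesions share an arm. Part of its apparent power under patient-level allocation comes from its inflated type I error.

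**The case against.** **The unit of allocation is not settled.** Calling each lesion a case and planning a fixed number of lesions per arm would also fit one envelope per lesion, and the sentence about assigning patients may be routine wording. On that reading nothing fails, as the last simulation row shows. This stands in part: the fault is conditional. But the only explicit statement of who is assigned names patients, so the wording favours the reading under which the planned test can fail.

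**Enrolling 79 per arm gives a margin.** The primary endpoint is measured at the procedure, so loss to follow-up should not remove it, though failed or abandoned resections could. With all 79 evaluable, a valid test keeps 90% power up to a design effect of about 79/70.1 = 1.127, and two of the four clustered cases stay above 90%. That is correct for power, but the protocol rests its 90% on 71 and assigns the excess to dropout. The margin also does nothing for type I error, because extra lesions do not repair a standard error that ignores clustering.

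**The size is unknown and may be trivial.** This stands. Patients with two lesions of 20–60 mm may be uncommon, and nothing in the protocol supports 40% of patients or a correlation of 0.7. That row shows an extreme and is not an expectation.

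**An unseen analysis plan might add a clustered analysis.** That is possible, but it would then contradict the counting rule and the tests fixed here.

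**Conclusion.** The concern holds. Read as written, the protocol allocates patients and then counts and tests lesions as if they were independent. With a shared arm and positive within-patient correlation, the primary test exceeds its 5% type I error, and 71 lesions per arm do not give a valid test 90% power.

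The direction is certain under those two conditions; the size cannot be found from the document. Over the lower three assumed cases, type I error is 5.3% to 7.0% and valid-test power at 71 per arm is 89.5% to 85.5%; the extreme case gives 9.8% and 78.5%. With no multi-lesion patients, no correlation, or separate randomisation of each lesion, the plan performs as stated. It should be fixed because it bears on the validity of the primary test and the repair is cheap.

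**What to change.** 1. **Randomization:** state that the patient is randomised, with one envelope per patient, and that all of a patient's study lesions take the same arm. This matches the Intervention section. If the sponsor in fact randomises each lesion separately, the protocol must say so; the planned test then keeps its error rate and power.
2. **Statistical analysis:** for lesion-level outcomes, use a linear mixed model with a random patient intercept for continuous outcomes such as resection speed, or GEE with patient as the cluster, which also covers binary outcomes such as R0 and en-bloc resection. Both are available in SPSS 26. Alternatively, analyse one prespecified index lesion per patient, at slightly lower power. Report post-procedural adverse events per patient.
3. **Sample Size:** state that 90% power at 71 lesions per arm assumes one lesion per patient or no within-patient correlation, and give the lower figure otherwise (for example 85.5% for a valid test at 20% and 0.5).
4. **Optional, to keep 90% for the valid test:** state an assumed share and correlation and inflate by the design effect. At 10% and 0.5: 70.1 × 1.091 = 76.5, so 77 per arm, and 77/0.9 gives 86. At 20% and 0.5: 70.1 × 1.167 = 81.8, so 82, and 82/0.9 gives 92. Starting from the rounded 71 gives 78 and 87, or 83 and 93.

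The cost is protocol wording, a different procedure in the same software and a slightly less favourable power statement. No extra patients are needed unless step 4 is taken. The envelope rule should be settled as early as possible, and the analysis before unblinded data are examined.

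### Randomization is stratified by center, but the stated test of resection speed leaves center out, which costs some precision if centers differ in mean speed

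*Protocol*

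**What the plan says.** The Randomization section reads "Stratified randomization by center". The Location entry under Methods names three hospitals.

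The Statistical analysis section gives one rule for all continuous variables. If normally distributed, they are "compared between groups using independent-samples t-tests"; if not, they are "compared with the Wilcoxon rank-sum test". The primary outcome, resection speed in mm²/min, is continuous, so this rule governs it. No analysis in the protocol uses center. The only stratified analysis is by lesion location, after the overall comparison (Outcome parameters).

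The Sample Size section takes its means and SDs from one site: "Based on a pilot study of 20 cases at our center". It then states that "the required sample size is 71 lesions per arm (142 total") and, after a 10% dropout allowance, "we plan to enroll 79 lesions per arm".

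**The concern.** When allocation is stratified by a factor, the analysis would normally carry that factor. If mean speed differs between hospitals, through operators or case mix, a test without center leaves that variation in its error term. The confidence interval is then wider than it needs to be, and a real difference is easier to miss.

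The planning SD makes this relevant. It comes from one center, so it cannot contain between-center variation, whereas the trial runs at three.

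This is not simply a detail left to an SAP. The protocol names the tests, and an SAP that added center would depart from the stated method.

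**Working it through.** **Inputs from the Sample Size section.** Means 27.2 and 21.1, difference 6.1; SDs 9.8 and 12.2; α = 0.05 (two-sided, from Statistical analysis); power 0.90; 71 per arm, 79 with dropout.

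**Assumed.** The share R of total variance that lies between centers. The protocol does not give it. I use 2%, 5% and 10%, with 20% as an upper-range value.

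**Step 1: reproduce the plan's figure.**
- Pooled SD = √((9.8² + 12.2²)/2) = 11.065.
- Standardized difference = 6.1/11.065 = 0.551.
- SE at 71 per arm = 11.065 × √(2/71) = 1.857; noncentrality = 6.1/1.857 = 3.28.
- Noncentral-t power on 140 df = 0.904. At 70 per arm it is 0.899, so 71 is the smallest adequate n.
- 71/0.90 = 78.9, rounded up to 79; 2 × 79 = 158.

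The stated sizes are correct for the unadjusted t-test. At 79 evaluable per arm, power is 0.931.

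**Step 2: width of the interval.** The unadjusted SE uses the total SD and the adjusted SE the within-center SD. The width ratio is 1/√(1−R).

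**Step 3: power if 11.065 is the within-center SD.** Total SD = 11.065/√(1−R).
- Arms not balanced within center: noncentral-t power with the total SD.
- Arms balanced within center: the difference varies with the within-center SD but is judged against the total SD. At 71 per arm, power ≈ Φ((6.1 − 1.977 × SE_total)/SE_within). For R = 10%: SE_total = 11.66 × √(2/71) = 1.957, and (6.1 − 3.869)/1.857 = 1.201, giving 0.885.

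| R | Total SD | Between-center SD | CI width ratio | Unadjusted power, 71, balanced | 71, not balanced | 79, balanced | 79, not balanced |
|---|---|---|---|---|---|---|---|
| 2% | 11.18 | 1.6 | 1.010 | 0.901 | 0.898 | 0.929 | 0.926 |
| 5% | 11.35 | 2.5 | 1.026 | 0.896 | 0.889 | 0.925 | 0.919 |
| 10% | 11.66 | 3.7 | 1.054 | 0.885 | 0.872 | 0.917 | 0.904 |
| 20% | 12.37 | 5.5 | 1.118 | 0.859 | 0.831 | 0.896 | 0.869 |

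With center in the model, power stays at about 0.90 (71 per arm) or 0.93 (79) at every share. Without balance, 79 per arm gives exactly 0.90 at R = 0.114.

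**Step 4: power if 11.065 is already the total SD.** The within-center SD is then 11.065 × √(1−R). At 71 per arm, unadjusted power is at least 0.904. Adjusted power is 0.909, 0.917, 0.930 and 0.954 for the four shares.

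**Step 5: type I error from omitting center.**
- With balance, the test is conservative: 2 × (1 − Φ(1.96/√(1−R))) = 0.044, 0.039 and 0.028 at 5%, 10% and 20%. Simulation (three near-equal centers, 20,000 runs per setting) gave 0.046, 0.040 and 0.028.
- Without balance, simulation gave 0.048 to 0.051.

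**Step 6: price of the center term if centers do not differ.** Simulated power at 71 per arm was 0.895 adjusted against 0.900 unadjusted without balance, and 0.902 against 0.903 with balance. That is half a point or less.

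**The case against.** The strongest reply is that nothing here is invalid and the loss may be trivial. Every loss figure rests on an assumed share. The operators are selected ("All ESD procedures were performed by experienced endoscopists", with minimum case numbers), which argues against large differences between hospitals. Full enrollment absorbs a share up to about 11%, and if the pilot SD already equals the trial's total SD, planned power is met without adjustment. All of this stands, and it is why the severity is low.

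A second reply is that covariate adjustment is usually settled in an SAP and that the rule in the protocol is generic. This stands in part: the rule does not single out the primary endpoint. It does, however, name the tests that apply to it, and neither uses center.

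Third, stratification is meant to balance arms within center, so the balanced figures deserve at least equal weight. Agreed; blocking is not stated, so both sets are shown.

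Two stronger readings are tempting. A reader might infer that the trial is underpowered or its sample size wrong. The documents do not support that: 71 and 79 reproduce, and a shortfall appears only under assumed center differences. A reader might instead infer that any positive result is safe because the test errs on the cautious side. That goes too far as well. The type I statement covers the omission of center only. The Sample Size section counts several lesions in one patient as separate cases, and neither the t-test nor a center term deals with their correlation.

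**Conclusion.** The point holds as a modest loss of precision, conditional on centers differing in mean speed. For shares of 2% to 10%, the interval is about 1% to 5% wider than necessary (12% at 20%). With 71 per arm and the pilot SD taken as within-center, the loss is up to about 2 power points with balanced arms and about 3 without (0.904 against 0.885 and 0.872 at a 10% share). If centers do not differ there is no loss.

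These figures rest on the assumed shares and on a pilot SD that is itself imprecise: its 95% CI is about 8.4 to 16.4, assuming 18 df from the 20 cases. The power values are therefore illustrative; the width ratios do not depend on that SD.

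**What to change.** In the Statistical analysis section, state that the single primary analysis is a linear model of resection speed on arm and center, reported as the adjusted mean difference with its 95% CI, and that it is used whatever any normality test shows. State that the t-test and a rank test are supportive only, with no data-driven switch of the primary method.

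This takes two sentences. Center is known for every lesion, so no new data, extra patients or change to the allocation lists or sample size is needed. The price is two degrees of freedom. How lesions from the same patient are handled is a separate matter that this change does not settle.
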